Secondary outcomes: The sample size of the entire trial is based on the primary outcome; the power to find a statistically significant difference for secondary outcome is limited to the total number of participants. For safety outcomes, we do not expect to find statistically different results between groups on SAEs. For toxicological outcomes of ENDS, such as measures of urinary biomarkers, we will compare participants based on ENDS exposure. Table 11.2-1 presents the number of participants we expect to fall into each category of ENDS and cigarette smoking over follow-up. In the intervention group, we expect that 19% of smokers would quit and 30% would use of ENDS at the 6-month follow-up.⁹ In the control group, we expect that 12% of smokers who quit at 6-month follow-up. Though participants in the control group will not be actively provided with ENDS during the first 6 months of the study, we expect 5% will purchase ENDS on their own.

Table 11.2-1: Expected distribution of participants over follow-up

Group	Intervention group					Control group					Legend:
	Ai	Bi	Ci	Di	Ei	Ac	Bc	Cc	Dc	Ec	
ENDS	+	+	-	-		+	+	-	-		Ai= ENDS use, stop smoking, intervention
Tob smk	-	+	-	+		-	+	-	+		Bi= ENDS use, smoking, intervention
Baseline		586							586		Ci= No ENDS, stop smoking, intervention
											Di= No ENDS, smoking, intervention
											Ei= Lost to follow-up (LTFU), intervention
6 months: N	56	111	50	340	29	11	17	56	473	29	Ac= ENDS use, stop smoking, control
% of group	10%	20%	9%	61%	5%	2%	3%	10%	85%	5%	Bc= ENDS use, smoking, control
12 months: N	49	93	38	365	41	11	16	44	474	41	Cc= No ENDS, stop smoking, control
% of group	9%	17%	7%	67%	7%	2%	3%	8%	87%	7%	Dc= No ENDS, smoking, control
24 months: N	37	79	32	380	59	11	16	26	475	59	Ec= LTFU, control
% of group	7%	15%	6%	72%	10%	2%	3%	5%	90%	10%	

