For measures of carcinogenicity, such as measures of incomplete combustion agents (VOCs and PAH: 1-OHP, 1- and 2-NAPH in urine)^{29,30} and exposure to TNSAs (NNK and NNN in urine),¹⁸ and measures of oxidative stress in urine (8-OHdG and 8-isoprostane),^{41, 91, 164} and MN in buccal epithelium, we will compare groups that stopped smoking with or without ENDS in intention to treat analyses (Ai+Ci vs. Ac+Cc; 112 vs. 70) and in per protocol analyses (Ai+Ac vs. Ci+Cc; 65 vs. 117). Based on previous cross sectional studies contrasting past smokers to smokers,^{52, 164, 165} we estimate a 48% power to detect significant differences between quitters and continuing smokers for 8-OHdG and 100% for 8-isoprostane between baseline and follow-up, at alpha 0.05 and an assumed correlation between baseline and follow-up of 0.7 (Table 11.2-2). We will perform 3 determinations of buccal MN on 2000 cells for each participant. Based on published results,^{99, 100, 166-168} we expect a baseline frequency among non-smokers of 0.74 MNs per thousand cells and a between-subject GSD of 1.3. We will have 80% power to detect a significant difference between smokers and non-smokers for a frequency ratio (FR) of 1.5.

For the 6-months changes in cardiovascular risk factors, we do not have direct data from RCT of ENDS use. Using data from previous RCT on nicotine replacement therapy, we expect a mean increase in HDL-cholesterol of 0.107 mmol/l (95% confidence interval 0.057 to 0.158 mmol/l) among quitters,⁵⁴ an increase in systolic blood pressure of 1.65 mm Hg and in diastolic blood pressure of 0.90 mm Hg after 6 months in quitters.^{55, 56} Considering data from the CoLaus study, a study on cardiovascular risk factors in a random sample of the Lausanne population, we expect to only have a 10 to 40% chance to detect a difference between ENDS users and continuing smokers.¹⁶⁹ We expect to be able to have 100% power to detect changes in respiratory symptoms.^{8, 170}

We do not expect to have adequate power to detect changes in incidence of cancer. However, we will apply strict open access rules and post the data on rigorous and systematic assessment of self-reported cancer in an online repository to enable the international community to pool results with other datasets and answer more definite answers on these important outcomes

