Table 11.2-2: Power calculation and sample size required to detect statistically significant differences between past- and current smokers for secondary outcome measures

Measure	Matrix	Non smoker	Past smoker	Current smoker	Reference	Power * N **	
		Mean (SD)	Mean (SD)	Mean (SD)			
Inhaled compounds							
1-OHP	Urine [µg/g creat]	0.08 (0.11)	0.11 (0.11)	0.2 (0.25)	Bartolomé et al. 2015 ¹⁷¹	98%	37
	Urine [µg/g creat]		0.04 (0.002)	0.12 (0.005)	Naufal et al. 2011 ¹⁷²	100%	2
1-naphtol	Urine [ng/g creat]		1.6 (0.1)	7.2 (0.4)	Naufal et al. 2011 ¹⁷²	100%	2
2-naphtol	Urine [ng/g creat]		1.8 (0.05)	8.9 (0.5)	Naufal et al. 2011 ¹⁷²	100%	2
Oxydative stress							
8OHdG	Urine [ng/mg creat]	2.75 (1.6)	3.62 (2.41)	4.24 (3.3)	Sauvain et al., 2011 ¹⁶⁴	48%	174
	EBC [ng/ml]	0.36 (0.09)	0.31 (0.10)	0.52 (0.15)	Doruk et al., 2011 ⁹¹	100%	3
8-isoprostane F2a	Urine [µg/g creat]	0.51 (0.04)	0.74 (0.07)	1.1 (0.1)	Harman et al., 2003 ⁵²	100%	2
	Urine [µg/g creat]	0.7 (2.7)		4.48 (2.7)	Seet et al., 2011 ⁴³	100% [†]	5
	EBC [pg/ml]	10.8 (0.8)		24.3 (2.6)	Montuschi et al., 2000 ⁸⁹	100% [†]	2

*Power to detect statistically significant difference between quitters (past smokers) and continuing smokers (current smokers) between baseline and follow-up at alpha 0.05, an assumed correlation between baseline and follow-up of 0.7 and 182 participants (112 vs. 70) for urine analyses.

† Calculations above in * based on data from never smokers compared to current smokers.

** Number of participants per group needed to detect statistically significant differences at alpha of 0.05 and beta (power) of 0.80.

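### Protocol 9.0, Table 11.2-2: biomarker power for quitters v continuing smokers uses two groups of quitters (112 v 70), so 48% for 8-OHdG and 98% for 1-OHP are wrong

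*Supplement*

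**What the plan says.** Protocol 9.0, section 11.2 (secondary outcomes), plans for the carcinogenicity and oxidative-stress markers: "we will compare groups that stopped smoking with or without ENDS in intention to treat analyses (Ai+Ci vs. Ac+Cc; 112 vs. 70"), and the same "in per protocol analyses (Ai+Ac vs. Ci+Cc; 65 vs. 117"). By the legend of Table 11.2-1, Ai, Ci, Ac and Cc have all stopped smoking.

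The next sentence turns to a different comparison: "we estimate a 48% power to detect significant differences between quitters and continuing smokers for 8-OHdG and 100% for 8-isoprostane". The footnote to Table 11.2-2 repeats that label, "difference between quitters (past smokers) and continuing smokers (current smokers) between baseline and follow-up", and gives the basis as "an assumed correlation between baseline and follow-up of 0.7 and 182 participants (112 vs. 70) for urine analyses". The table's power and N columns use past-smoker and current-smoker means and SDs.

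Table 11.2-1 in protocol 9.0 expects these numbers at 6 months:
- Intervention arm: Ai 56, Bi 111, Ci 50, Di 340, lost 29.
- Control arm: Ac 11, Bc 17, Cc 56, Dc 473, lost 29.

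**The concern.** The effect size comes from one comparison (past v current smokers) and the group sizes from another (quitters in one arm v quitters in the other). A power figure built that way describes neither.

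The table also conflicts with itself. Its N column asks for 174 per group for 80% power on 8-OHdG. The protocol expects 173 quitters and 941 continuing smokers, which is practically the required number on one side and more than five times it on the other, yet the stated power is 48%.

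Two things are at stake. The plan tells readers that 8-OHdG has about an even chance of separating quitters from smokers, when by its own inputs it is well powered. And because 112 v 70 is also the size given for the contrast of quitters by arm, a reader could carry the table's percentages over to a contrast for which the protocol assumes no effect size. SAP 2.0 does not fill the gap: these urinary markers are not among its core secondary outcomes (6.1), and further outcomes are placed outside its scope (6.7).

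**Working it through.** **Inputs.** All come from protocol 9.0, section 11.2.
- Urinary 8-OHdG (ng/mg creatinine): past smokers 3.62 (SD 2.41), current smokers 4.24 (SD 3.3); difference 0.62.
- Urinary 1-OHP (µg/g creatinine), the row with 98% power: past smokers 0.11 (SD 0.11), current smokers 0.20 (SD 0.25); difference 0.09.
- Correlation 0.7, alpha 0.05 taken as two-sided.

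**Formula.** SE = √[(1 − 0.7²)(s₁²/n₁ + s₂²/n₂)], with 1 − 0.49 = 0.51. Power = Φ(difference/SE − 1.96).

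**1. Reproducing the plan's figures.** Give the 112 past-smoker values and the 70 current-smoker values.
- 8-OHdG: 2.41²/112 + 3.3²/70 = 0.0519 + 0.1556 = 0.2074; SE = √(0.51 × 0.2074) = 0.325; 0.62/0.325 = 1.906; power 47.9% (stated 48%).
- 1-OHP: SE = 0.0226; 0.09/0.0226 = 3.98; power 97.8% (stated 98%).
- N per group at 80% power = 0.51 × (s₁² + s₂²) × 2.80²/difference²: 173.9 and 36.9 (stated 174 and 37).

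All four match. The 8-OHdG variants tried do not: roles swapped 53.4%, equal groups of 91 52.7%, change score 42.0%, follow-up value only 27.5%, one-sided test 60.3%, paired change in 182 quitters 94.4%. So the 70 control-arm quitters stand in for continuing smokers.

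**2. Counts in the current Table 11.2-1.**

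| Group | Sum | Current | Text or footnote |
|---|---|---|---|
| Intervention quitters | 56 + 50 | 106 | 112 |
| Control quitters | 11 + 56 | 67 | 70 |
| Quitters using ENDS | 56 + 11 | 67 | 65 |
| Quitters not using ENDS | 50 + 56 | 106 | 117 |
| All quitters | 106 + 67 | 173 | 182 |
| Continuing smokers | 111 + 340 + 17 + 473 | 941 | not used |

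The text and footnote figures fit the table in protocol 2.0 (59 + 53 = 112; 6 + 64 = 70) and were not updated with it.

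**3. The labelled comparison with the right groups, 173 v 941.**
- 8-OHdG: 2.41²/173 + 3.3²/941 = 0.0336 + 0.0116 = 0.0451. With baseline adjustment SE = 0.152, 0.62/0.152 = 4.09, power 98.3%. Without it (factor 1 instead of 0.51) SE = 0.212, ratio 2.92, power 83.1%.
- 1-OHP with baseline adjustment: SE = 0.0083, ratio 10.8, power above 99.9%.

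**4. Quitters by arm (106 v 67) or by ENDS use (67 v 106).** Section 11.2 gives no expected difference, so no power figure follows from the documents. Assume the past-smoker SD of 2.41 on both sides and the same 0.51:
- SE = 2.41 × √0.51 × √(1/106 + 1/67) = 0.269.
- Difference with 80% power: 2.80 × 0.269 = 0.75 ng/mg, or 1.2 times the 0.62 gap.
- An observed difference of 1.96 × 0.269 = 0.53 reaches significance.
- Power is about 64% for a true difference of 0.62 and about 21% for half of it, 0.31.

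**The case against.** The best defence is that little hangs on these numbers. The sample size rests on the primary outcome, and section 11.2 says that power for secondary outcomes is limited by the number of participants. Section 11.4 promises effect estimates with 95% confidence intervals, which will show imprecision directly. For the labelled comparison the error understates power. All of this stands and sets the weight of the point; none of it makes 112 v 70 the right group sizes.

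Three stronger readings are tempting, and the documents do not support them.
- *The table claims 48% to 100% power for quitters with v without ENDS.* It does not. The table title, the footnote and the sentence in the text all say past v current smokers or quitters v continuing smokers. Only the shared 112 v 70 invites that inference.
- *Among quitters, only an 8-OHdG difference above the whole smoker-quitter gap could be detected.* The 0.75 is the difference with 80% power, not a detection limit; an observed 0.53 would be significant. 8-OHdG is also the noisiest urinary marker in the table. By the same method the 80%-power difference is about 38% of the gap for this 1-OHP source and about 6% for 8-isoprostane (the row with past-smoker values).
- *The stated percentages serve no planned analysis.* Section 11.4.3 plans to compare groups by exposure to tobacco smoking and ENDS, which can cover quitters v continuing smokers. The label is plausible; the group sizes are wrong.

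It is also fair to say that 98% is conditional. It takes urine from everyone followed up, counts the 128 dual users (111 + 17) as ordinary continuing smokers, and relies on cross-sectional SDs and an assumed correlation. Leaving the dual users out (173 v 813) still gives about 98%. Missing urine would lower it.

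**Conclusion.** The point holds for protocol 9.0. The 48% for 8-OHdG and 98% for 1-OHP are wrong for the comparison they name, because both groups used are quitters. With the protocol's own current counts, 8-OHdG power is about 98% with baseline adjustment at a correlation of 0.7 and about 83% without; 1-OHP power is over 99% with adjustment. This rests on complete urine collection among those followed, dual users counted as continuing smokers, and the table's means and SDs. The counts in the text and footnote are stale as well, though that alone matters little: keeping the same mistake with 106 v 67 would move 48% only to 46%.

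The contrast of quitters by arm or by ENDS use has no power figure in the protocol. The 0.75 ng/mg for it rests on the assumed SD of 2.41 in both groups. The consequence is moderate: it affects how secondary biomarker results are planned and read, and nothing in the primary analysis.

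**What to change.** In protocol 9.0, section 11.2 and Table 11.2-2:
1. Replace 182 (112 v 70) in the footnote by 173 v 941 for quitters v continuing smokers. Restate 8-OHdG power as about 98% with baseline adjustment at a correlation of 0.7 (about 83% without) and 1-OHP as over 99% with adjustment. State the assumptions on urine availability and dual users.
2. Update the text counts to 106 v 67 (by arm) and 67 v 106 (by ENDS use).
3. Add a sentence that the table does not apply to quitters compared by arm or by ENDS use. Give for that contrast the 8-OHdG difference with 80% power, about 0.75 ng/mg, with power of about 64% at 0.62 and 21% at 0.31, and name the SD assumption.

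The cost is one table footnote, a few figures and a few sentences. Conduct, data collection and the sample size of 1172 do not change.

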11.3 Statistical criteria of termination of trial

Not applicable as no formal interim analysis is planned.

11.4 Planned Analyses

The statistical analysis of the main results of the trial will be done at CTU Bern by a statistician blinded to the allocation. After the start of the trial but before recruitment ends, a statistical analysis plan will be written. The plan will determine all necessary data preparation steps (e.g. additional validations, generation of new variables), definitions (e.g. analysis sets), and statistical analyses (e.g. models, outputs such as tables and graphs).

All statistical analyses will be presented as effect measure plus 95% confidence interval. A significance level of 5% will be used.

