Tobacco smoke upregulates inflammatory pathways and downregulates anti-inflammatory pathways.^{36, 115, 116} Tobacco smoke also generates reactive oxygen species and may recruit phagocytes that generate free radicals, possibly contributing to airway and other pathologies by disturbing the balance between free radicals and antioxidants and inducing oxidative stress.³⁶⁻³⁸ Most of the damage tobacco smoke causes is derived mainly by inhaling pyrolyzed tobacco and other organic components.¹¹⁷ Replacing tobacco cigarettes with ENDSs thus decrease user exposure to toxicants and carcinogens; the components of the aerosol and of traditional cigarette smoke differ significantly, and also have different effects on inflammation and oxidative stress. Assessing the effects of ENDS on the full range of inflammatory biomarkers will help understand the effect of ENDS on health, including unforeseen outcomes. Blood samples will be analyzed with Olink Proteomics' unique protein detection system,¹¹⁸ the Proximity Extension Assay (PEA), which allows us to perform highly specific and sensitive multiplex immunoassays to detect 92 inflammation-related protein biomarkers.

Scientific impact

Despite the ready availability of ENDS in Europe and the USA, at local stores and on the Internet, there are significant gaps in our knowledge. These devices have been commercially available for less than a decade, and only gained popularity in the last few years. They are also evolving rapidly. No researchers have independently evaluate the effectiveness, safety, toxicological profile, and effect on health-related outcomes of ENDS in the setting of a randomized controlled trial. Doing so would help Swiss and international policymakers make evidence-based decisions about the safety profile of ENDS.

Data on exposition to potential toxins from ENDS in daily life.

We will inform smokers interested in quitting with ENDS, and policymakers, about the toxins measured in the urine and blood of participants who use ENDS for smoking cessation under real life conditions. While data on the safety and risk-benefit profile of ENDS appear promising under laboratory conditions,^{5, 6} ENDS does release some toxins. To opponents of ENDS, the small amount of released toxins in

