4.3 Secondary Objectives

Secondary objectives are to assess the effect of using ENDS on exposure to inhaled toxic compounds and assess the effect of ENDS use on health-related outcomes, including clinical health-related outcomes (respiratory symptoms, pulmonary function,, olfactory function, inflammatory biomarkers) and surrogate health-related outcomes (oxidative stress, cardiovascular risk factors, micronuclei in mouth epithelium).

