- CVRFs assessed by HDL- and LDL-cholesterol, triglycerides, HbA1c (only for participants with diabetes), creatinine, blood pressure levels, heart rate, waist circumference and body mass index.
- Pulmonary function, measured by conventional pulmonary function tests and by the more

sensitive techniques of multiple breath washout and MRI

- Micronuclei assessment in buccal epithelium
- Olfactory function assessment (olfactory identification score (OIS)). Cut-off for hyposmia 11 points, cut-off for anosmia 8 points.
- "Dry-hit" recognition at 6 month-follow up
- Inflammatory biomarkers

12- and 24- months follow-up:

- Validated 7-day point prevalence abstinence. Confirmation of having smoked no cigarettes in the past seven days, validated by urinary levels of NNAL. If NNAL is missing, validation by urinary levels of anabasine or exhaled CO.
- Validated 7-day point prevalence abstinence. Confirmation of having smoked no cigarettes in the past seven days, validated by urinary levels of NNAL. If NNAL is missing, validation by urinary levels of anabasine or exhaled CO.
- Self-reported 7-day point prevalence abstinence. Self-report of having smoked no cigarettes in the past seven days.
- Continuous smoking abstinence. Self-report of having smoked no cigarettes from quit date, validated by urinary levels of anabasine. If anabasine is missing, validation by exhaled CO.
- Continuous smoking abstinence. Self-report of having smoked no cigarettes from TQD, validated by urinary levels of NNAL. If NNAL is missing, validation by urinary levels of anabasine or exhaled CO.
- Self-reported smoking abstinence allowing a 2-week`grace period'. Smoking abstinence allowing a 2-week`grace period' after the TQD.
- Validated smoking abstinence allowing a 2-week`grace period'. Smoking abstinence allowing a 2-week`grace period' after the TQD, validated by urinary levels of anabasine. If anabasine is missing validation by exhaled CO.
- Validated smoking abstinence allowing a 2-week`grace period'. Smoking abstinence allowing a 2-week`grace period' after the TQD, validated by urinary levels of NNAL. If NNAL is missing, validation by urinary levels of anabasine or exhaled CO.
- Self-reported smoking abstinence allowing up to 5 cigarettes. Smoking abstinence allowing up to 5 cigarettes in total after the TQD.

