For the "dry-hit" recognition, voluntary participants will be given two ENDS at the 6 months follow-up visit – one with correct filling of the e-liquid and one with a too low e-liquid level and therefore producing a "dry hit" which would be recognized as a burnt smell when vaping. They are asked to assess which one is the ENDS producing a "dry-hit". Both ENDS will be filled with a tobacco flavored e-liquid without nicotine (0mg/ml). The participants will be instructed to take at least 1 puff of 2 seconds (maximum of 4 puffs of 2 seconds each with a 30 second break in-between) from each ENDS. Participants will not be informed about the sequence of the ENDS. Participants are allowed to go back and forth between the two ENDS before they decide. After their decision, they will be informed, if they were able to recognize the ENDS which generates a "dry hit". The inflammatory biomarkers will be measured in blood serum using Olink Proteomics' unique protein detection system,¹¹⁸ the Proximity Extension Assay (PEA), which allows us to perform highly specific and sensitive multiplex immunoassays to detect 92 inflammation-related protein biomarkers.

Several questionnaires will be used to assess further parameters:

- Demographics: Age, gender; Socio-economic: education level, marital status; medical history, including medication use and healthcare utilization.
- Smoking history,^{155, 156} including Fagerström questionnaire to assess nicotine dependence¹⁵⁷ and the Minnesota nicotine withdrawal scale.¹⁵⁸
- Physical activity (International Physical Activity Questionnaire, IPAQ)¹³⁸
- legal and illegal drug use: Alcohol consumption (AUDIT-C)^{141, 159}, illegal drug use (cannabis, cocaine, other)¹⁴²
- Quality of life (EQ-5D questionnaire)¹⁴⁴
- Depression symptoms (PHQ-9)¹⁶⁰
- Anxiety (GAD-7)¹⁴⁶
- Sleep Quality (PSQI)¹⁴³
- Environmental pollution exposure (e.g. second hand smoke)^{147, 148}

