11.4.3 Secondary Analyses

We will repeat the calculations described in 11.4.2 for the secondary smoking cessation outcomes. To test the effect of ENDS on reducing the number of cigarettes smoked per day, we will define a binary predictor of >50% smoking reduction from baseline to follow-up smoking and repeat the analyses for the main outcome of quitting. We will also use joint multivariate random-effects (JMRE) models allowing to model CPD and smoking cessation. In addition, we will use mixed linear effect model to analyze the change in CPD modelled as a continuous outcomes over time.

We will present modified per-protocol sensitivity analyses, in particular for participants in the control group who might have started using ENDS in the first six months.

For the measures of changes in measures of urinary biomarkers, exhaled breath measures, CVRFs and respiratory symptoms and pulmonary function from baseline to the 6-months visit, we will first compare the changes in these measures between the intervention and control group using two-sample t-tests or Wilcoxon rank-sum test, whenever appropriate. We will then fit univariate and multivariate mixed linear effect models. We will use multivariate linear and multinomial logistic regression models to compare groups according to their exposure to tobacco smoking and ENDS.

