4.1 Confidence intervals and *P* values

All applicable statistical tests will be 2-sided and will be performed using a 5% significance level. Estimates and effect measures will be presented with a two-sided 95% confidence interval.

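### The 92-protein inflammation panel is listed as one secondary outcome with no multiplicity rule; if each protein is tested at the stated 5%, false positives are likely under no effect

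*Supplement*

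**What the plan says.** Protocol 9.0, section 5.2, has a single line among the 6-month secondary outcomes: "Inflammatory biomarkers". Section 4.3 also names the panel among the health-related outcomes of the secondary objectives ("olfactory function, inflammatory biomarkers"). Section 9.2.2 shows what that line contains: "multiplex immunoassays to detect 92 inflammation-related protein biomarkers". Section 3.1 gives the purpose: "Assessing the effects of ENDS on the full range of inflammatory biomarkers will help understand the effect of ENDS on health, including unforeseen outcomes".

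The measurement is a firm commitment. It is scheduled at baseline and month 6 (9.1), assigned to Bern, Geneva and St. Gallen (9.2), and has its own funding (14.1).

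On error control, section 11.4 says: "All statistical analyses will be presented as effect measure plus 95% confidence interval. A significance level of 5% will be used". SAP 2.0, section 4.1, adds sidedness: "All applicable statistical tests will be 2-sided and will be performed using a 5% significance level". Section 11.4.3 lists the measures to be compared by t-test or Wilcoxon test and then by mixed models ("For the measures of changes in measures of urinary biomarkers, exhaled breath measures, CVRFs and respiratory symptoms and pulmonary function from baseline to the 6-months"). The blood inflammatory proteins are not in that list.

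SAP 2.0 does not include the panel in its core secondary outcomes (6.1). It leaves separately registered subprojects and further outcomes outside its scope (6.7). Its section 7 says that analyses of additional outcomes are described in the protocol and will not be specified further in the SAP.

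**The concern.** One line in the outcome list stands for 92 results, and the stated aim is to look across all of them, including for effects nobody has predicted. Such a screen needs a rule for telling a signal from the best of many chance findings. A flat 5% level does not supply one.

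The panel is meant to inform a disputed question, namely whether vaping raises or lowers inflammation relative to the control strategy. Without a family-wide rule, an isolated protein that appears raised, or one that appears lowered, is an ordinary result when nothing is happening. Either could be read as evidence of harm or of benefit. SAP 2.0 (2.8 and Table 4) also records that a study team aware of allocation took over all analyses, so a rule fixed beforehand is worth more here than usual.

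**Working it through.** The documents state no family-wise error rate, so there is no figure of theirs to reproduce.

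**Inputs from the documents**
- Number of proteins: m = 92 (protocol 9.2.2).
- Level: 0.05 (protocol 11.4), two-sided (SAP 2.0, 4.1), so the critical value is 1.96.

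**Assumptions not in the documents**
- One between-arm test per protein.
- No true effect on any protein.
- A common correlation rho between the test statistics, varied from 0 to 0.8.

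**Expected false positives**, whatever the correlation: 92 × 0.05 = 4.6.

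**At least one false positive, independent proteins:** 1 − (1 − 0.05)^92 = 1 − 0.95^92 = 0.991.

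**At least one false positive, common correlation rho.** Write each statistic as z = √rho · U + √(1 − rho) · e, with U shared by all proteins and e specific to each. Given U = u, one protein stays inside ±1.96 with probability

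q(u) = Φ((1.96 − √rho · u)/√(1 − rho)) − Φ((−1.96 − √rho · u)/√(1 − rho)).

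The required chance is 1 − ∫ φ(u) · q(u)^92 du, integrated numerically:

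| Assumed rho | Chance of at least one p < 0.05 |
|---|---|
| 0 | 99.1% |
| 0.1 | 98.5% |
| 0.2 | 96.8% |
| 0.3 | 93.1% |
| 0.4 | 86.4% |
| 0.5 | 75.9% |
| 0.6 | 62.7% |
| 0.7 | 48.7% |
| 0.8 | 35.2% |

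**Variations**
- Four blocks of 23 proteins, correlated only within blocks (simulated): 90.8% at within-block rho 0.5 and 65.7% at 0.8.
- Only 70 proteins detectable and independent: 1 − 0.95^70 = 97.2%.
- Three or more false positives among 92 (exact binomial at rho 0, simulation otherwise): 84% at rho 0, 60% at 0.3 and 41% at 0.5.

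**Under a family-wide rule, still with no true effect**
- Benjamini-Hochberg at 5%, 20,000 simulated null panels: chance of any claim 5.1%, 4.5% and 3.5% at rho 0, 0.3 and 0.5.
- Bonferroni, for scale, at 0.05/92 = 0.00054 per protein: 4.9%, 4.1% and 2.9% at the same correlations.

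**The case against.** The strongest reply is that the plan does not say what the calculation assumes. A reader might infer that the protocol commits to testing each of the 92 proteins at 5%, and that the trial would therefore report a changed protein in 75% to 99% of null repetitions. The documents do not support that.

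- Section 11.4.3 does not name the panel, so one test per protein is only the natural reading of a general rule that covers all analyses.
- Nothing says that one p-value below 0.05 would be announced as an effect on inflammation.
- The lower figure of 75% requires a common correlation of no more than about 0.5. The documents do not state one, and stronger correlation takes the chance down to 35%.

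There is also a scope argument. SAP 6.7 sets separately registered subprojects aside. Separate funding and collection at three of the five sites fit a subproject with a plan of its own, and the stated purpose sounds exploratory. Such a plan may exist. The documents neither cite one nor identify the panel as such a subproject, and SAP section 7 sends the reader of additional outcomes back to the protocol, where only the 5% level is found.

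Finally, Benjamini-Hochberg is one of several sound choices. A panel score, a global test, a lead protein or an explicit exploratory label would also serve. An error rule would also leave the model and the contrast for the panel still to be written.

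These points limit how firmly the size can be stated and what can be attributed to the plan. They do not remove the gap: a listed secondary outcome made of 92 results has no rule for judging them together.

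**Conclusion.** The point holds as a gap in the plan. Protocol 9.0 makes a 92-protein screen a single secondary outcome, and the only level stated for it in either current document is an unadjusted 5%.

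The size is conditional on one test per protein between arms, no true effect on any protein, and an unknown correlation. Over the range tried, the chance of at least one false positive runs from 99% down to 35%. Even the lowest value is about seven times the nominal 5% (35.2/5 = 7.0), so the conclusion does not depend on the correlation chosen. Comparisons by exposure group or additional models would push the chance up, and dropping undetectable proteins would lower it slightly.

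The consequence is confined to how the panel is interpreted. The primary cessation outcome and its analysis are not touched. The change should be made, but it does not threaten the trial's main conclusion.

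**What to change.** Add to protocol section 11.4: the 92 inflammatory proteins are analysed as one family, with the Benjamini-Hochberg false discovery rate held at 5%; all 92 estimates are reported with 95% confidence intervals and adjusted p-values; a protein is called changed only if its adjusted p-value is below 0.05. If a separate plan for the panel exists, cite it there and put the rule in it.

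It would be sensible to name the panel in 11.4.3 at the same time, with its model and contrast, so that the family of 92 tests is defined.

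The cost is a short addition to the text and one line of code, with no new data. The drawback is lower power for any single protein. The unadjusted estimates and intervals stay visible, so nothing is hidden from readers who want to follow up an individual marker.
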